6. One (1) subject enrolled at Dose Level 6 is not evaluable and 0 of the other 2 subjects enrolled at Dose Level 6 experience a DLT. Following the table in Section 16.3.1 (looking at the column for 2 evaluable subjects treated at the current dose), dose escalation is allowed and the next 3 subjects (Subjects #9, #10 and #11) are enrolled at Dose Level 7.

7. One (1) of the 3 subjects enrolled at Dose Level 7 experience a DLT, so following the table in Section 16.3.1, the next 3 subjects (Subjects #12, #13 and #14) are also enrolled at Dose Level 7.
8. Of the 6 total subjects enrolled at Dose Level 7, 1 subject is not evaluable and only 1 of the other 5 subjects experience a DLT. Following the table in Section 16.3.1 (looking at the column for 5 evaluable subjects treated at the current dose), dose escalation is allowed and the next 3 subjects (Subjects #15, #16 and #17) are enrolled at Dose Level 8.
9. Two (2) of the 3 subjects enrolled at Dose Level 8 experience a DLT, so following the table in Section 16.3.1, de-escalation is required and the next 3 subjects (Subjects #18, #19 and #20) are enrolled at Dose Level 7. An additional subject was available for treatment (Subject #21), so was included in the cohort as well (i.e., 4 subjects are enrolled at Dose Level 7).
10. Of the 10 total subjects enrolled in Dose Level 7, 1 subject is not evaluable and only 1 of the other 9 subjects experience a DLT. Following the table in Section 16.3.1 (looking at the column for 9 evaluable subjects treated at the current dose), dose escalation is allowed and the next 3 subjects (Subjects #22, #23 and #24) are enrolled at Dose Level 8.
11. Four (4) of the 6 total subjects enrolled at Dose Level 8 experience a DLT, so following the table in Section 16.3.1, Dose Level 8 is eliminated from the trial. This means that subjects will no longer be enrolled in Dose Level 8, 9 or 10. De-escalation is required and the next 3 subjects (Subjects #25, #26 and #27) are enrolled at Dose Level 7.
12. The maximum sample size of 42 subjects has not been reached, but 12 subjects have now been enrolled at Dose Level 7, so dose escalation can stop early and the MTD can be determined based on the 27 subjects enrolled.

Scenario #4:

1. Subject #1 is enrolled at Dose Level 1 in a single subject cohort. Subject #1 is not evaluable. Because the one subject enrolled at the dose level is not evaluable, another subject (Subject #2), is enrolled at Dose Level 1 in a single subject cohort.
2. Subject #2 does not experience a DLT or a \geq Grade 2 toxicity, so dose escalation is allowed and Subject #3 is enrolled at Dose Level 2 in a single subject cohort.
3. Subject #3 experiences a DLT, so 2 additional subjects (Subjects #4 and #5) are enrolled at Dose Level 2. **NOTE:** Having a \geq Grade 2 toxicity no longer guides dose escalation (only DLTs do) and subsequent cohorts will now include at least 3 subjects.
4. Two (2) of the 3 total subjects enrolled at Dose Level 2 experience a DLT, so following the table in Section 16.3.1, de-escalation is required and the next 3 subjects (Subjects #6, #7 and #8) are enrolled at Dose Level 1.
5. Of the 5 total subjects enrolled at Dose Level 1, 2 subjects are not evaluable and 0 of the other 3 subjects experience a DLT. Following the table in Section 16.3.1 (looking at the column for 3 evaluable subjects treated at the current dose), dose escalation is allowed and the next 3 subjects (Subjects #9, #10 and #11) are enrolled at Dose Level 2.
6. Two (2) of the 6 total subjects enrolled at Dose Level 2 experience a DLT, so following the table in Section 16.3.1, the next 3 subjects (Subjects #12, #13 and #14) are also enrolled at Dose Level 2.

7. Of the 9 total subjects enrolled at Dose Level 2, 1 subject is not evaluable and 3 of the other 8 subjects experience a DLT. Following the table in Section 16.3.1 (looking at the column for 8 evaluable subjects treated at the current dose), de-escalation is required and the next 3 subjects (Subjects #15, #16 and #17) are enrolled at Dose Level 1.
8. Of the 8 total subjects enrolled at Dose Level 1, 2 subjects are not evaluable and 3 of the other 6 subjects experience a DLT. Following the table in Section 16.3.1 (looking at the column for 6 evaluable subjects treated at the current dose), de-escalation is required. However, since Dose Level 1 is the lowest dose level, and since the boundary for elimination has not been reached, the next 3 subjects (Subjects #18, #19 and #20) are also enrolled at Dose Level 1.
9. Of the 11 total subjects enrolled in Dose Level 1, 2 subjects are not evaluable and 5 of the other 9 subjects experience a DLT. Following the table in Section 16.3.1 (looking at the column for 9 evaluable subjects treated at the current dose), Dose Level 1 is eliminated from the trial. This means that subjects will no longer be enrolled in Dose Level 1. Since this is the lowest dose level, the trial is stopped for safety and no dose is selected as the MTD.

16.3.1.4 Keyboard Design Scenarios – Schedule 2

If schedule 2 is opened, the table in Section 16.3.1 will be used for all dose escalation decisions and the same principles demonstrated in Scenarios #1-4 apply with the following exceptions:

1. All cohorts will include at least 3 subjects (there are no single subject cohorts).
2. Because there are no single subject cohorts, \geq Grade 2 toxicities do not guide dose escalation.
3. The maximum total sample size is 15 subjects.

Reference:

16.4 Deauville Criteria

Score	PET/CT scan result
1	No uptake
2	Uptake \leq mediastinum
3	Uptake $>$ mediastinum but \leq liver
4	Uptake moderately higher than liver
5	Uptake markedly higher than liver and/or new lesions
X	New areas of uptake unlikely to be related to lymphoma

Reference: Barrington SF, et al. Role of imaging in the staging and response assessment of lymphoma: consensus of the International Conference on Malignant Lymphomas Imaging Working Group. J Clin Oncol. 2014;32(27):3048-3058.

16.5 Cockcroft-Gault Formula for Creatinine Clearance

$$\text{Creatinine clearance (mL/min)}^1 = \frac{Q \times (140 - \text{age [yr]}) \times \text{ideal body weight [kg]}^2}{72 \times \text{serum creatinine [mg/dL]}}$$

Q = 0.85 for females

Q = 1.0 for males

OR

$$\text{Creatinine clearance (mL/min)}^2 = \frac{K \times (140 - \text{age [yr]}) \times \text{ideal body weight [kg]}^1}{\text{serum creatinine } [\mu\text{mol/L}]}$$

K = 1.0 for females

K = 1.23 for males

1. Creatinine clearance has a maximum value of 125 mL/min.
2. Use ideal body weight (IBW) if body weight > 30% of IBW. Otherwise, use bodyweight

Calculation of IBW using the Devine Formula [Devine, 1974]:

Males = $50.0 \text{ kg} + (2.3 \times \text{each inch over 5 ft})$ or $50.0 \text{ kg} + (0.906 \text{ kg} \times \text{each cm over 152.4 cm})$

Females = $45.5 \text{ kg} + (2.3 \times \text{each inch over 5 ft})$ or $45.5 \text{ kg} + (0.906 \text{ kg} \times \text{each cm over 152.4 cm})$

Example:

Male, actual body weight = 90.0 kg; height = 68 inches; IBW = $50 + (2.3)(68 - 60) = 68.4 \text{ kg}$

This subject's actual body weight is >30% over IBW. Therefore, in this case, the subject's IBW of 68.4 kg should be used in calculating the estimated creatinine clearance

Reference:

Devine BJ. Case Number 25 Gentamicin Therapy: Clinical Pharmacy Case Studies. Drug Intell. Clin Pharm. 1974;8:650-655.

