Absolute neutrophil count (ANC)	$\geq 1.5 \times 10^9/\text{L}$ without growth factor support

Platelet count	$\geq 50 \times 10^9/L$
Hemoglobin (Hgb)	$> 9.0 \text{ g/dL}$ with no blood transfusions for at least 5 days prior to D1 of IP.
Creatinine clearance (CrCl)	$\geq 30 \text{ milliliter (mL)/min}$ (using modified Cockcroft-Gault formula; Appendix Section 16.5)
ALT/AST	$\leq 3 \times \text{ULN}$
Total bilirubin	$\leq 1.5 \times \text{ULN}$; subjects with isolated indirect hyperbilirubinemia are permitted if direct bilirubin ratio is $<35\%$ and total bilirubin is $\leq 3.0 \times \text{ULN}$
Left ventricular ejection fraction (LVEF) by ECHO	\geq Lower limit of normal (LLN) per institutional threshold If LLN is not defined for a given institution, then ejection fraction must be $\geq 50\%$

10. Females of child bearing potential (FCBP) must have a negative serum or urine pregnancy test within 72 hours of D1 of IP. **NOTE:** FCBP unless they are surgically sterile (i.e., have undergone a complete hysterectomy, bilateral tubal ligation/occlusion, bilateral oophorectomy or bilateral salpingectomy), have a congenital or acquired condition that prevents childbearing or are naturally postmenopausal for at least 12 consecutive months (see Appendix Section 16.2 for additional details). Documentation of postmenopausal status must be provided. FCBP should use an acceptable method of contraception (see Appendix Section 16.2) to avoid pregnancy during treatment and for 30 days (which exceeds 5 half-lives) after the last dose of IP. FCBP must start using acceptable contraception at least 14 days prior to D1 of IP.
11. Male subjects with female partners must have azoospermia from a prior vasectomy or underlying medical condition or agree to use an acceptable method of contraception during treatment and for 30 days (which exceeds 5 half-lives) after last dose of SL-279252 (see Appendix 16.2). Male subjects of reproductive potential must start using acceptable contraception at least 14 days prior to D1 of treatment with SL-279252 as per Appendix Section 16.2.
12. All AEs resulting from prior anti-cancer immunotherapy have resolved (**NOTE:** exceptions include alopecia, vitiligo, and endocrinopathies adequately treated with hormone replacement).
 - Subjects that were discontinued from prior PD-1/L1 therapy due to immune-related adverse events are not eligible

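### Appendix 16.5, which defines the CrCl ≥ 30 mL/min entry limit, has a female µmol/L constant that disagrees with its other three constants and a weight footnote that conflicts with its own worked example

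*Protocol*

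**What the plan says.** Protocol 4.2, criterion 9, sets the renal limit at 30 mL/min or more and fixes the method: "using modified Cockcroft-Gault formula; Appendix Section 16.5". Protocol 4.1 and Section 6 allow no waivers, so the calculated value decides entry.

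Appendix 16.5 gives two formulas joined by a bare OR, one for creatinine in mg/dL and one for µmol/L.

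- **Constants.** The mg/dL formula has "Q = 0.85 for females" and 1.0 for males. The µmol/L formula has "K = 1.0 for females" and 1.23 for males.
- **Weight.** Both numerators are labelled as ideal body weight (IBW). The footnote reads: "Use ideal body weight (IBW) if body weight > 30% of IBW. Otherwise, use bodyweight".
- **Worked example.** The subject is "Male, actual body weight = 90.0 kg; height = 68 inches". The example gives the reason "This subject's actual body weight is >30% over IBW" and concludes that the "IBW of 68.4 kg should be used in calculating the estimated creatinine clearance".

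**The concern.** The two formulas should return the same clearance for the same person, because they differ only in the unit of creatinine. If the constants do not agree, eligibility depends on which unit the local laboratory reports. The schedule-of-assessments footnotes send clinical laboratory tests to local laboratories, the synopsis lists sites in four countries, and nothing says which formula a site must use.

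The footnote and the example state different conditions for switching to ideal weight: above 30% of IBW, and more than 30% over IBW. Clearance is proportional to the weight entered, so the choice can move a subject across the limit. At stake is consistent application of a hard entry criterion: two sites could decide differently on the same patient while each points to the printed text.

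**Working it through.** **Reproducing the worked example.** IBW = 50 + 2.3 × (68 − 60) = 68.4 kg. The ratio is 90.0 / 68.4 = 1.316, so the subject is 31.6% over IBW, as the example states. The figure reproduces.

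**Female constant.** Inputs, all from Appendix 16.5: Q = 0.85 (female), Q = 1.0 (male), K = 1.23 (male), K = 1.0 (female), divisor 72.

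- mg/dL: CrCl = Q × (140 − age) × weight / (72 × creatinine).
- µmol/L: CrCl = K × (140 − age) × weight / creatinine.
- Equating the two male formulas gives the implied unit conversion: 1.23 × 72 = 88.56 µmol/L per mg/dL.
- The matching female constant is 0.85 × 88.56 / 72 = 0.85 × 1.23 = 1.0455.
- With K = 1.0, the µmol/L result is 1 / 1.0455 = 0.956 of the mg/dL result, about 4.4% low.
- A woman at exactly 30.0 mL/min by mg/dL gets 30 × 0.956 = 28.7 by µmol/L. To reach 30 by µmol/L she needs 30 × 1.0455 = 31.4 by mg/dL.

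Sensitivity: with a conversion of 88.4, which is an assumption and not in the documents, the female constant is 0.85 × 88.4 / 72 = 1.044. The shortfall is then 4.2% and the band ends at 31.3. The male constant would be 88.4 / 72 = 1.228, within 0.2% of the printed 1.23, so the male pair agrees under either conversion.

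Illustration (assumed woman, age 70, 60 kg entered, 1.6 mg/dL):

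- mg/dL: 0.85 × 70 × 60 / (72 × 1.6) = 31.0, eligible.
- µmol/L: 70 × 60 / (1.6 × 88.56) = 29.6, not eligible (29.7 with 88.4).

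**Weight rule.** For the 68-inch man in the example:

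| Reading | Use IBW when weight exceeds |
|---|---|
| Footnote, literally | 0.30 × 68.4 = 20.5 kg |
| Worked example | 1.30 × 68.4 = 88.9 kg |

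At 90 kg both readings select 68.4 kg, so the example's numerical result does not separate them; only its stated reason does. Below 88.9 kg they differ. The literal result equals the actual-weight result multiplied by IBW / actual weight. For a subject at 30.0 on actual weight:

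| Actual weight / IBW | Literal footnote gives (mL/min) |
|---|---|
| 0.8 | 30 / 0.8 = 37.5 |
| 1.1 | 30 / 1.1 = 27.3 |
| 1.3 | 30 / 1.3 = 23.1 |

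Both directions, for an assumed 70-year-old man of 68 inches:

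- 54.7 kg, 2.0 mg/dL: 70 × 54.7 / (72 × 2.0) = 26.6 by the example's rule (not eligible); 70 × 68.4 / 144 = 33.25 by the literal footnote (eligible).
- 80 kg, 2.4 mg/dL: 70 × 80 / (72 × 2.4) = 32.4 by the example's rule (eligible); 70 × 68.4 / 172.8 = 27.7 by the literal footnote (not eligible).

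**The case against.** The strongest reply concerns the weight rule. The example sits directly beneath the footnote and gives its reason in words: "actual body weight is >30% over IBW". The footnote's closing clause, which sends everyone else to actual weight, would have no function on the literal reading. A careful reader would recover the intended rule. This stands. A reader might infer that the appendix applies ideal weight to every subject; the documents do not support that, because the example contradicts it.

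What remains is a wording defect that is not quite harmless. The numerator label in both formulas agrees with the literal footnote, and no example shows a subject for whom actual weight is used. Someone working from the formula and footnote alone would get ideal weight each time.

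A second reply is that the female constant errs on the conservative side and touches a narrow band. That is also correct, and it limits the severity. It does not remove the error, which depends on no reading of the text.

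**Conclusion.** Both inconsistencies are real, and both are minor.

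- **Female constant.** It is wrong relative to the appendix's other three constants, by about 4.4% (4.2% under the assumed conversion). It excludes women at about 30.0 to 31.4 mL/min by mg/dL if their site uses µmol/L. It cannot admit anyone below the limit, and men are unaffected.
- **Weight footnote.** It conflicts with the worked example. The apparent intent can be recovered, but a literal reading could reverse eligibility in either direction near 30 mL/min.

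A reader might go further and conclude that subjects with inadequate renal function are being admitted to the dose-limiting toxicity cohorts. The documents do not show this. It would require a site to follow the footnote against the example, and nothing indicates that any site did. The documents give no distribution of clearance, sex, body weight or laboratory unit, so the number of subjects affected by either inconsistency cannot be computed. The individual patients above are illustrations with assumed values.

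Sample size, error rates and the primary analysis are unaffected.

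**What to change.** In Appendix 16.5:

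1. Set the female µmol/L constant to 1.05, so that it agrees with the other three (0.85 × 1.23 = 1.0455). Rounding to two decimals, as for the male constant, leaves a difference of 1.05 / 1.0455 = 1.004, or 0.4%.
2. Reword the weight footnote to match the worked example: IBW only when actual weight is more than 30% above IBW (over 1.3 × IBW), and actual weight in all other cases.
3. Label both numerators as weight in kg, with the footnote attached.

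The cost is a few words in one appendix at the next amendment, plus a check of any site or database calculation built from it. No new data are needed, and neither the design nor the analysis changes.

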16.6 RECIST 1.1 and iRECIST Criteria

16.6.1 RECIST 1.1 Criteria

Measurable disease: Measurable tumor lesions (nodal, subcutaneous, lung parenchyma, solid organ metastases) are defined as those that can be accurately measured in at least one dimension (longest diameter to be recorded) as ≥ 10 millimeter (mm) with CT scan or clinical examination. Bone lesions are considered measurable only if assessed by CT scan and have an identifiable soft tissue component that meets these requirements (soft tissue component ≥ 10 mm by CT scan). Malignant lymph nodes must be ≥ 15 mm in the short axis to be considered measurable; only the short axis will be measured and followed. All tumor measurements must be recorded in mm (or decimal fractions of cm). Previously irradiated lesions are not considered measurable unless progression has been documented in the lesion.

Malignant lymph nodes: pathological nodes must meet the criterion of a short axis of ≥ 15 mm by CT scan and only the short axis of these nodes will contribute to the baseline sum. All other pathological nodes (those with short axis ≥ 10 mm but < 15 mm) should be considered non-target lesions. Nodes that have a short axis < 10 mm are considered non-pathological and should not be recorded or followed.

Non-measurable disease: All other lesions (or sites of disease), including small lesions (longest diameter < 10 mm [< 1 cm] or pathological lymph nodes with ≥ 10 to < 15 mm [≥ 1 to < 1.5 cm] short axis), are considered non-measurable disease. Bone lesions without a measurable soft tissue component, leptomeningeal disease, ascites, pleural/pericardial effusions, lymphangitis cutis, inflammatory breast disease, lymphangitic involvement of lung or skin, and abdominal masses followed by clinical exam are all non-measurable. Lesions in previously irradiated areas are non-measurable, unless progression has been demonstrated.

Note: Cystic lesions that meet the criteria for radiographically defined simple cysts should not be considered as malignant lesions (neither measurable nor non-measurable) since they are, by definition, simple cysts.

‘Cystic lesions’ thought to represent cystic metastases can be considered as measurable lesions, if they meet the definition of measurability described above. However, if non-cystic lesions are present in the same participant, these are preferred for selection as target lesions.

Target lesions: When more than one measurable tumor lesion is present at baseline all lesions up to a maximum of 5 lesions in total (and a maximum of 2 lesions per organ), representative of all involved organs, should be identified as **target lesions** and recorded and measured at baseline. Target lesions should be selected on the basis of their size (lesions with the longest diameter), be representative of all involved organs, but in addition should be those that lend themselves to reproducible repeated measurements. It may be the case that, on occasion, the largest lesion does not lend itself to reproducible measurement in which circumstance the next largest lesion which can be measured reproducibly should be selected. A sum of the diameters (longest for non-nodal lesions, short axis for nodal lesions) for all target lesions will be calculated and reported as the baseline sum diameters. If lymph nodes are to be included in the sum, then only the short axis is

added into the sum. At baseline, the sum of the target lesions (longest diameter of tumor lesions plus short axis of lymph nodes: overall maximum of 5) is to be recorded.

After baseline, a value should be provided on the eCRF for all identified target lesions for each assessment, even if very small. If extremely small and faint lesions cannot be accurately measured but are deemed to be present, a default value of 5 mm may be used. If lesions are too small to measure and indeed are believed to be absent, a default value of 0 mm may be used. The baseline sum diameters will be used as reference to further characterize any objective tumor regression in the measurable dimension of the disease.

Non-target lesions: All non-measurable lesions (or sites of disease) plus any measurable lesions over and above those listed as target lesions are considered **non-target lesions** and should also be recorded at baseline. Measurements of these lesions are not required, but the presence, absence, or in rare cases unequivocal progression of each should be noted throughout follow-up.

16.6.2 Evaluation of Response

Complete Response (CR): Disappearance of target and non-target lesions and normalization of tumor markers. Pathological lymph nodes must have short axis measures <10 mm (Note: continue to record the measurement even if <10 mm and considered CR). Residual lesions (other than nodes <10 mm) thought to be non-malignant should be further investigated (by cytology, specialized imaging or other techniques as appropriate for individual cases) before CR can be accepted. Response should be confirmed in a subsequent scan ≥ 4 weeks after the scan showing CR.

Partial Response (PR): At least a 30% decrease in the sum of the measures (longest diameters for tumor lesions and short axis measure for nodes) of target lesions, taking as reference the baseline sum of diameters. Non-target lesions must be non-progressive disease. Response should be confirmed in a subsequent scan ≥ 4 weeks after the scan showing PR.

Stable Disease (SD): Neither sufficient shrinkage to qualify for PR nor sufficient increase to qualify for progressive disease, taking as reference the smallest sum diameters while on study. Documented at least once ≥ 4 weeks from baseline.

Progressive Disease (PD): At least a 20% increase in the sum of diameters of measured lesions taking as references the smallest sum of diameters recorded on study (including baseline) AND an absolute increase of ≥ 5 mm. Appearance of new lesions will also constitute progressive disease (including lesions in previously unassessed areas). In exceptional circumstances, unequivocal progression of non-target disease may be accepted as evidence of disease progression, where the overall tumor burden has increased sufficiently to merit discontinuation of treatment or where the tumor burden appears to have increased by at least 73% in volume. Modest increases in the size of one or more non-target lesions are NOT considered unequivocal progression. If the evidence of progressive disease is equivocal (target or non-target), treatment may continue until the next assessment, but if confirmed, the earlier date must be used.

16.6.3 iRECIST 1.1 Criteria

When using iRECIST, the definitions of measurable and non-measurable lesions still follow RECIST 1.1. The principles used to establish an objective tumor response when using iRECIST are largely unchanged from RECIST 1.1, however, responses assigned using iRECIST have a prefix of “i” (e.g., “immune” complete response [iCR]) to differentiate them from responses assigned using RECIST 1.1.

The major change is the concept of resetting the bar if RECIST 1.1 progression is followed at the next assessment by tumor shrinkage. This adaptation accounts for instances where an increase in tumor burden, or the appearance of new lesions, does not reflect true tumor progression. Therefore, iRECIST requires confirmation of progression.

Confirming Progression: iRECIST requires the confirmation of progression and uses the terms iUPD (unconfirmed progression) and iCPD (confirmed progression). Confirmatory scans should be performed at least 4 weeks after iUPD. iCPD is confirmed if further increase in tumor burden, compared to the last assessment, is seen as evidenced by one or more of the following criteria:

- Continued increase in tumor burden (from iUPD) where RECIST 1.1 definitions of progression had been met (from nadir) in target, non-target disease or new lesions.
 - Progression in target disease worsens with an increase of at least 5 mm in the absolute value of the sum
 - Continued unequivocal progression in non-target disease with an increase in tumor burden
 - Increase in size of previously identified new lesion (s) (an increase of at least 5 mm in the absolute value of the sum of those considered to be target new lesions) or additional new lesions
- RECIST 1.1 criteria are met in lesions types (target or non-target or new lesions) where progression was not previously identified, including the appearance of additional new lesions.
- If iUPD is not confirmed at the next assessment, then the appropriate response will be assigned (iUPD if the criteria are still met, but no worsening, or iSD, iPR or iCR if those criteria are met compared to baseline).

New Lesions: New lesions should be assessed and measured as they appear using RECIST 1.1 criteria (maximum of 5 lesions, no more than 2 per site, at least 10 mm in long axis (or 15 mm in short axis for nodal lesions) and recorded as New Lesions-Target (NLT) and New Lesion-Non-Target (NLNT) to allow clear differentiation from baseline target and non-target lesions.

New lesions may either meet the criteria of NLT or NLNT to drive iUPD (or iCPD). However, the measurements of target lesions should NOT be included in the sum of measures of original target lesions identified at baseline. Rather, these measurements will be collected on a separate table in the eCRF.

Progressive disease is confirmed in the New Lesion category if the next imaging assessment, conducted at least 4 weeks (but not more than 8 weeks) after iUPD confirms further progression from iUPD with either an increase of at least 5 mm in the absolute value of the sum of NLT OR an increase (but not necessarily unequivocal increase) in the size of NLNT lesions OR the appearance of additional new lesions.

iRECIST Time Point Response Table

Target Lesions	Non-Target Lesions	New Lesions	Time Point Response (TPR)	
			No prior iUPD	Prior iUPD
iCR	iCR	No	iCR	iCR
iCR	Non-iCR/Non-iUPD	No	iPR	iPR
iPR	Non-iCR/Non-iUPD	No	iPR	iPR
iSD	Non-iCR/Non-iUPD	No	iSD	iSD
iUPD with no change OR decrease from last TP	iUPD with no change OR decrease from last TP	Yes	NA	NLs confirms iCPD if NL were previously identified and increase in size (≥ 5 mm in SOM for NLT or any increase for NLNT) or number. If no change in NLs (size or number) from last TP, remains iUPD
iSD	iUPD	No	iUPD	Remains iUPD unless iCPD confirmed based in further increase in size of NT disease (need not meet RECIST 1.1 criteria for unequivocal PD)
iUPD	iUPD	No	iUPD	Remains iUPD unless iCPD confirmed based on: further increase in SOM of at least 5 mm, otherwise remains iUPD
iUPD	iUPD	No	iUPD	Remains iUPD unless iCPD confirmed based on further increase in: previously identified T lesion iUPD SOM ≥ 5 mm and/or NT lesion iUPD (prior assessment need not be unequivocal PD)

Target Lesions	Non-Target Lesions	New Lesions	Time Point Response (TPR)	
			No prior iUPD	Prior iUPD
iUPD	iUPD	Yes	iUPD	Remains iUPD unless iCPD confirmed based on further increase in: 
 • previously identified T lesion iUPD SOM ≥ 5 mm and/ • previously identified NT lesion iUPD (prior assessment need not be unequivocal PD) • size or number of new lesions previously identified
Non-iUPD/PD	Non-iUPD/PD	Yes	iUPD	Remains iUPD unless iCPD confirmed based on: 
 • increase in size or number of new lesions previously identified
* Using RECIST 1.1 principles. If no pseudo-progression of disease (PSPD) occurs, RECIST 1.1 and iRECIST categories for CR, PR and SD would be the same. ** in any lesion category. *** previously identified in assessment immediately prior to this TP. PD = progressive disease; SOM = sum of measurements Note: Participants with a global deterioration of health status requiring discontinuation of treatment without objective evidence of disease progression at that time should be reported as " symptomatic deterioration ." Every effort should be made to document the objective progression even after discontinuation of treatment.				

